1.0 PROTOCOL SUMMARY AND/OR SCHEMA

Rationale: The majority of patients with perihilar cholangiocarcinoma (PHC) have locally advanced disease {LAD} upon presentation or exploratory laparotomy; for this reason, they are not suitable candidates for curative resection[1]. Additionally some of the patients develop locally advanced recurrence during their course of disease. Therefore, in most patients with this type of biliary tract cancer, only palliative concepts can be offered. ERCP guided and/or percutaneous transhepatic biliary drainage offer the best survival, because in combination with sufficient drainage, reduction of tumor masses in the lumen of the bile duct was shown to prolong patient survival[2]. Effectiveness of photodynamic therapy (PDT) was investigated in two randomized controlled and a few controlled studies[3-8]. But these studies failed to prove efficacy with clear impact on clinical outcomes. Moreover, PDT has not become part of normal clinical practice because it causes skin phototoxicity lasting for 3-4 weeks and requires technology not available at most centers. Other thermal ablative methods, such as radiofrequency ablation, are affected by a heat-sink effect when tumors are located close to vascular structures, such as the liver hilum, which can limit effectiveness, and there are concerns with injuries to biliary and vascular structures in treating these areas. These limitations may be overcome by irreversible electroporation {IRE}, which is a non-thermal tissue ablation method that has been used to treat liver tumors in over 60 patients at MSK. By exposing cancer cells to a sufficient electric field by IRE, cell plasma membranes are disrupted and cells undergo apoptotic or necrotic cell death[9, 10]. Therefore, IRE is considered as non-thermal ablation technique and is currently applied to treat liver tumors where thermal ablation techniques are contraindicated.

Objective: This study will investigate the outcomes of IRE for the treatment of unresectable, locally advanced PHC..

Study design: A single center phase II study.

Study population: 20 patients with locally advanced PHC deemed unresectable due to preoperatively determined primary tumor characteristics and/or distant lymph node metastases (N2) or due to discovery of unresectability on exploratory laparotomy.

Main study endpoints:

The primary outcome is patency of biliary drainage. In patients with plastic percutaneous drains this is defined as ability to remove plastic biliary drains within 1.5 months of the IRE procedure without need for reinsertion of a drain or stent. For patients with metal stents in place the definition of patent biliary drainage is 4-months without cholangitis post IRE procedure.

Secondary outcomes are the success rate of completing IRE (defined as percentage of planned pulses completed}, complications, duration of hospital stay, quality of life, impact of IRE on post-procedural CT imaging and blood biomarker response, time between IRE and start of palliative chemotherapy, metal stent patency, progression-free and overall survival. Prolonged hospital stay is defined as hospital stay for more than 10 days. The average length of stay for major liver procedures is 8 days. Patients with hilar cholangiocarcinomas often have biliary drains and stents so require extra care as inpatients after any procedure. Complications will be defined as patients experiencing a clinically relevant IRE-related complication within 30 days post-IRE, defined as CTCAE (version 5.0} grade

3 or higher complications requiring re-intervention, prolonged hospital stay, intensive care admission, re-admission or leading to mortality.

Follow up: 30 days after intervention for the primary endpoint. For survival endpoints, there is a 2-year followup.

2.1 OBJECTIVES AND SCIENTIFIC AIMS

Primary objective:

The primary objective of this study is to assess patency of biliary drainage. In patients with plastic percutaneous drains this is defined as ability to remove plastic biliary drains within 1.5 months of the IRE procedure without need for reinsertion of a drain or stent. For patients with metal stents in place the definition of patent biliary drainage is 4-months without cholangitis post IRE procedure.

Secondary objective:

The secondary outcomes of interest are

- Duration of hospital stay
- Complications
- Quality of life
- Tumor response on CT imaging and blood biomarker response
- Time between IRE and start of palliative chemotherapy
- Duration of palliative chemotherapy
- Progression-free and overall survival
- Success rate of completing IRE (defined as percentage of planned pulses completed)

3.0 BACKGROUND AND RATIONALE

Perihilar cholangiocarcinoma (PHC), also known as Klatskin tumor, is the most common type of bile duct cancer, with an annual incidence of 1 to 2 per 100,000 in Western countries. It arises at or near the confluence of the right and left main bile duct. Patients typically present with obstructive jaundice and are staged with cross-sectional imaging of the abdomen and chest. In the absence of metastatic disease, patients are eligible for resection with curative intent, which is the only treatment that confers a chance of long-term survival[11]. Five-year overall survival (OS) after resection varies from 13% to 40% across series with more than 100 patients[12]. The poor 5-year OS reflects a high recurrence rate of 49 to 76% after curative intent resection of PHC [13]. Only 50% of the patients were suitable candidates for surgery due to unresectability at presentation and another 40% are found to have locally advanced or metastatic disease during exploratory laparotomy. In patients with disease ultimately deemed unresectable, approximately half of tumors are considered locally advanced because of

unreconstructable vascular involvement or extensive biliary involvement. Liver transplantation in these cases is only performed in a few experienced centers worldwide with strict selection criteria and extensive preoperative work-up including neoadjuvant treatment. Unfortunately, high dropout rates up to 30% prior to transplantation are reported. Systemic chemotherapy is the mainstay of treatment for patients who are not candidates for curative resection or neoadjuvant therapy followed by liver transplantation. Traditionally, the preferred regimen has been the combination of gemcitabine and cisplatin and offers a median progression-free survival of 8 months and overall survival of 12 months [14]. The recently released results from the BILCAP randomized trial of adjuvant capecitabine compared to best supportive care showed an apparent lack of benefit in the hilar cholangiocarcinoma patients (HR 1.09; 95% CI 0.68, 1.71; ASCO 2018 abstract). Trials in patients with more advanced disease suffer from a lack of accrual of patients with locally advanced hilar cholangiocarcinoma, so we have to extrapolate from trials like BILCAP.

The goals of palliative biliary drainage are to relieve jaundice, prevent cholangitis and liver failure, and improve quality of life [15]. Biliary stents are not without risk and have been associated with occlusion, migration, cholecystitis, and tumor ingrowth and seeding [16]. Successful biliary drainage has obvious palliative advantages to leaving patients undrained due to the morbidity of untreated cholangitis. In addition, in one randomized trial of plastic vs. metal stents, there was a survival advantage with metal stents compared to plastic stents (due to longer patency rates) [17]. Metal stents are a more durable and cost-effective option as they have a patency superior to that of plastic stents, with patients requiring less frequent procedures (Table 1) [18]. Virbidity related to stents can occur even within 30 days of placement (39% plastic stents and 12% metal stents) [19]. Although the overall prognosis of unresectable PHC is poor, patients with locally advanced PHC or lymph node metastases

Table 1. Time of patency (months)

	Plastic stents	Metal stents	P value
Sanachan et al r171	10	3.0	<0.0001
Raiu et al r181	19	5.6	<0.0001

beyond the hepatoduodenal ligament have significant longer survival (14 to 16 months) compared to patients with organ metastases (3 to 5 months) [20]. 12% of these patients even survive for more than 36 months [20]. This particular subgroup of PHC patients with primary locally advanced disease may therefore benefit from ablative therapies that counteract tumor growth and potentially improve biliary stent patency and survival. In the past decade, several different ablative techniques like stereotactic body radiation therapy, photodynamic therapy (PDT), (intraductal) radiofrequency ablation (RFA), brachytherapy and microwave ablation have been investigated. Local tumor reduction by PDT in combination with stent therapy is effective for reducing cholestasis. For patients with unresectable hilar cholangiocarcinoma, two randomized studies and several controlled studies have shown an advantage in survival over stenting alone, given improved stent patency [21]. Furthermore, some trials demonstrated a gain in QoL or in performance status [4-7]. But PDT has major limitations such as skin phototoxicity for 3-4 weeks due to the use of slowly degradable photosensitizers in PDT [22]. In addition, thermal ablative modalities (i.e. RFA) are limited by the disadvantages of surrounding tissue heating causing strictures to bile ducts and thromboses to portal vein and

hepatic artery branches and the heat-sink effect. This effect is caused by blood flow in surrounding vessels creating an area where optimal temperatures are not reached, leaving viable cancer tissue *in situ* [23]. This is particularly challenging in PHC because of the typical location in the liver hilum near the portal vein and hepatic artery. Considering these limitations, there is a need to investigate new non-thermal ablative techniques in the treatment of locally advanced PHC.

IRE is FDA approved for soft tissue ablation. Bile duct cancers are considered soft tissue. The most extensively studied organ for use of IRE has been the liver and the liver hilum, where delicate structures in the hepatoduodenal ligament preclude intervention using thermal ablation techniques. Demonstration of lack of significant acute injury to hepatic vessels and bile ducts by the early work of Lee et al [24] has now been corroborated by several authors with confirmed safety with up to 8 weeks of follow-up [25, 26]. An overall complication rate of 16% has been recently described in a meta-analysis [27]. In a comparison, in a review on hepatic RF ablation in 3,670 patients, the overall complication rate was 9%, with rates of 7%, 10%, 10%, and 32% for percutaneous, laparoscopic, simple open, and combined open RF ablation [28].

In one study using serial computed tomography (CT) scanning, IRE lesions created around large hepatic veins showed minimal early narrowing, but with complete recovery over time and no evidence of late thrombosis or occlusion [26]. IRE around hilar bile ducts similarly showed overall resistance to significant injury, with some ducts exhibiting, at worst, clinically insignificant late strictures [29]. Three major studies have been published by our group at MSK in the past about irreversible electroporation in perivascular or peribiliary hepatic malignant tumors [30-32]. Silk et al [32] evaluated biliary complications after IRE of 19 liver metastases in nine patients within 1 cm of the common, left, or right hepatic duct. One patient showed subsegmental bile duct prominence without increased bilirubin; this still existed after 11 months, without progressive dilation or segmental atrophy. Retrospective review of computed tomography images showed that one needle was placed in direct contact with the bile duct. Two other patients showed bile duct dilation with increased bilirubin, for which one required stent placement; both conditions appeared to be secondary to tumor progression. Kingham et al [30] treated 28 patients with 65 tumors, of which most were located < 1 cm from a major hepatic vein or portal pedicle, similar to patients with PHC. The overall morbidity was 3%. Complications included 1 intraoperative arrhythmia and 1 postoperative portal vein thrombosis. There were no treatment-associated mortalities. At a median follow-up of 6 months, there was 1 tumor with persistent disease (1.9%) and 3 tumors recurred locally (5.7%) [30]. In the Netherlands, a phase II feasibility study of IRE in patients with advanced PHC (ALPACA-trial) was initiated this year [33]. A series of 26 patients with unresectable hilar cholangiocarcinoma was also recently published (V'artin et al, Safety and efficacy of irreversible electroporation in the treatment of obstructive jaundice in advanced hilar cholangiocarcinoma. HPB, 2018 in press). This retrospective review compared these patients to 137 patients with unresectable hilar cholangiocarcinoma who did not undergo IRE. The median catheter-free time in the IRE patients was 305 days (range 92-458 days). Of the 137 control patients, 80 (59%) had an admission for biliary drain infection, occlusion, or other catheter-related problem. This demonstrates

our hypothesis that IRE in patients with unresectable perihilar cholangiocarcinoma can prolong the stent patency and therefore prevent septic complications. In addition, only 2 of 26 patients had a grade 3 or higher complication.,

The demonstration of tissue structure sparing in the many organs (especially in the liver) supports the relative safety of IRE, and bodes well for this technology's potential. However, several investigators have pointed out the lack of complete understanding of how best to optimize IRE treatments in a variety of tissues, healthy, and neoplastic. Altering the treatment parameters of the energy transmitted to the tissue may produce zones of IRE as well as zones that may be subjected to additional effects including thermal damage, especially in tissue immediately surrounding an electrode. As demonstrated by the work of Faroja et al, tissue temperatures exceeding protein denaturation can be achieved by manipulation of certain dosing parameters. Recent work also showed differences in imaging and histopathology effects as a function of distance from the IRE electrode, with an immediate perielectrode zone that appeared to have more coagulative changes in contrast to the expected non-coagulative IRE zone marked by congestion. Choi et al. showed potential damage to the bile duct mural architecture when the IRE electrodes were immediately adjacent to the ducts. As a safety precaution, placement of electrodes <3 mm to central bile ducts should be avoided.

4.1 OVERVIEW OF STUDY DESIGN/INTERVENTION

4.2 Design

This is a prospective, single-center phase II study to look at the outcomes of RE with the use of NanoKnife® system (AngioDynamics, Queensbury, NY) in patients with preoperatively diagnosed locally advanced, unresectable PHC due to vascular or lymph node involvement, or those with potentially resectable tumors (those that are expected to be fully resectable before surgery) that appear intraoperatively to be locally advanced or metastasized to N2 lymph nodes at exploratory laparotomy.

4.3 Intervention

The study will evaluate the outcomes of using RE in patients with intraoperatively determined advanced unresectable PHC. The study will include data from 20 patients that have this IRE procedure performed as standard of care by hepatopancreatobiliary surgeons with experience using IRE.

5.0 THERAPEUTIC/DIAGNOSTIC AGENTS

The NanoKnife (AngioDynamics, Queensbury, NY) RE device will be used in all patients. The device is cleared by the US Food and Drug Administration for use in ablating soft tissue. The

RE device comprises a generator, a foot pedal, and 15- or 25-cm-long electrodes. The electrodes used to treat these patients have a tip length ranging from 5 to 40 mm. This distance represents the active tip of the electrode and the remainder of the needle is insulated. The RE device generates 1,500 to 3,000 V. Voltage is determined by a standard algorithm (AngioDynamics) that uses factors such as the intended size of the ablation zone, the number of probes, the distance between probes, and the length of the active electrode tip.[15] The size or shape of the tumor determines the number of electrodes used.

6.1 CRITERIA FOR SUBJECT ELIGIBILITY

The study population consists of 20 adult patients who are diagnosed with locally advanced, unresectable PHC. Unresectability will be established either preoperatively, based on imaging and other preoperative testing, or intraoperatively in patients undergoing planned exploratory laparotomy. Patients will be recruited at the outpatient clinic. In cases of a planned exploratory laparotomy, patients will be asked to participate in the study in case disease is deemed unresectable during surgery. These patients will undergo RE during the same operative session. Patients with unresectable tumors based on imaging at initial visit or preoperative workup, will be asked to participate in the study and receive RE via laparotomy. Prior to surgery, biopsies will be taken to verify perihilar cholangiocarcinoma. Patients with resectable PHC, PHC eligible for liver transplantation or organ metastasized PHC at surgical exploration will be excluded. The subject exclusion criteria outlined below is evaluated per standard of care for the RE procedure and as such is listed in this protocol.

6.2 Subject Inclusion Criteria

In order to participate in this study, a patient must meet all of the following criteria:

- Age 18 years or older
- Capable of providing written and oral informed consent in English

Meets criteria for unresectable disease:

- Locally advanced disease based on preoperative work-up demonstrating that the tumor is unresectable due to portal vein, hepatic artery, and/or bile duct involvement, insufficient hypertrophy response of the future liver remnant after portal vein embolization, or patients not able to tolerate major liver surgery
- Found to be unresectable intraoperatively based on vascular, biliary, or lymph node (N2) involvement upon exploratory laparotomy
- Patients will be assessed for chemotherapy prior to treatment with RE, but given the common problem of recurrent cholangitis, some patients will not be candidates for chemotherapy until after RE is performed.

6.3 Subject Exclusion Criteria

- Locally advanced PHC eligible and accepted for liver transplantation evaluation
- PHC with > 5 cm extension along the common hepatic duct or common bile duct on preoperative imaging or intraoperative ultrasound
- Metastases to peritoneum, liver or other organs confirmed by percutaneous biopsy, staging laparoscopy or intraoperative frozen section
- Lymph node metastases beyond N2 stations, confirmed by intraoperative frozen sections or radiographic diagnosis
- History of cardiac disease:
 - Congestive heart failure (NYHA class >2)
 - Active Coronary Artery Disease (defined as myocardial infarction within 6 months prior to screening)
 - Cardiac arrhythmias requiring anti-arrhythmic therapy or pacemaker (beta blockers are permitted)
- Implanted stimulation device (defined as implantable cardiac device and a pacemaker)
- Uncontrolled hypertension (blood pressure must be 160/95 mmHg at the time of screening on a stable antihypertensive regimen)
- Uncontrolled infections (> grade 2 NCI-CTC, version 3.0)
- Epilepsy
- Both narrowing (sclerosis) of the main portal vein and a reduced diameter of either the common hepatic artery, celiac trunk or superior mesenteric artery of >50%

7.0 RECRUITMENT PLAN

All patients will be recruited in outpatient clinic by one of our hepatopancreatobiliary (HPB) attendings ([name]). Full study information will be provided by the study physician or one of the investigators during the outpatient clinic appointment.

8.0 PRETREATMENT EVALUATION

Due to the nature of disease, patients with PHC undergo extensive pre-operative work-up (e.g., laboratory testing, CT or MR imaging, biliary drainage, liver function tests) prior to surgical exploration and potential portal vein embolization. In the present study, patients that will undergo open RE during exploratory laparotomy will have undergone these preoperative work-up procedures as standard of care. Additionally, Quality of life will be assessed during the pre-treatment visit using the Functional Assessment of Cancer Therapy-Hepatobiliary instrument (FACT-Hep). FACT-Hep is a 45-item self-report instrument designed to measure QoL in patients with hepatobiliary cancers. It comprises the FACT-General (FACT-G) and the hepatobiliary subscale (Hep). The FACT-G consists of 27 items that measure 4 domains of well being in cancer patients: physical well being (PWB), social/family well being (SWB),

functional well-being (FWB), and emotional well-being (EWB). The instrument employs a Likert-type format (0 "not at all" to 4 "very much"). Lower total scores reflect lower QoL. The FACT-G score is a total of the subscale scores. The FACT-G has demonstrated internal consistency, score stability, reliability, and validity [34-39]. The Hep is a reliable and validated disease-specific subscale consisting of questions relating to pruritus, jaundice, and drainage catheters [40,41]. Patients will not be replaced if they do not complete these questionnaires.

9.0 TREATMENT/INTERVENTION PLAN

Preoperative biliary drainage

Biliary drainage for malignant hilar strictures or masses is a complex procedure requiring considerable skill and experience. Candidates for IRE who initially present with potentially resectable PHC undergo preoperative biliary drainage as part of the standard preoperative work-up. In the present study, the exact approach of biliary drainage (i.e. endoscopically or percutaneously, specified liver segments, unilateral or bilateral) prior to surgery is decided by surgeon. A metal biliary stent is not considered a contraindication for IRE as long as a no-touch technique is pursued (i.e. IRE electrodes are not in contact with the metal stent).

Antibiotic prophylaxis

Antibiotic prophylaxis will be administered according to the MSKCC's protocol prior to biliary drainage and IRE. Patients will receive one 2g dose of Cefotetan IV, 30-60min prior to surgery. The same antibiotic will be used for the treatment of cholangitis (2g Cefotetan IV every 12 hours). In case of a patient allergy to Cefotetan, patients will receive Clindamycin/Gentamicin as alternative antibiotic treatment.

Intraoperative IRE procedure

Antibiotic prophylaxis is administered prior to the operation. During exploratory laparotomy, resectability of the tumor is assessed by the attending surgeon. When the tumor appears resectable, a resection will be performed. In case of non-nodal (extra)hepatic dissemination of the tumor, no procedure will be performed. In both cases the patients will be excluded from this study. Only when the tumor appears non-resectable, but non-metastasized, an IRE procedure will be performed. The IRE procedure will be performed under ultrasound guidance by the attending surgeon.

NanoKnife® device settings

The NanoKnife® IRE device (AngioDynamics, Queensbury, NY) will be used in this study in normal clinical fashion. This means the machine will be configured to deliver 90 pulses lasting one microsecond each, high-voltage (1500-3000 V) direct current (25-45 A) electrical pulses. Before administering the 90 one-microsecond therapeutic pulses, a test pulse at 270 V is delivered. Typically, 90 pulses will be delivered in 9 sets of 10 pulses between paired unipolar electrodes, with an exposed tip of 1.5-2.0 cm. The voltage setting for each electroporation will

be determined by the distance between each pair of electrodes and will be aimed at 1500 V/cm, with the intent to generate at least 1000 V between electrodes. The electrodes will be placed in and around the tumor under ultrasound guidance according to the manufacturer's guidelines, aiming at a macroscopically complete ablation with a 5 mm margin, with the inter-electrode distances 10-24 mm and a maximum angulation between electrodes of 15°. The predicted treatment zone will be automatically calculated using the NanoKnife generator software according to a system-based protocol that takes into account the exact position of all electrodes. The number of probes used for ablation is dependent on tumor size. If the lesion is larger or has a different shape than the area that one set of probes can cover (according to manufacturer's guidelines), multiple ablations will be performed, until the whole tumor area is ablated. Number of probes, number of probe replacements (per probe) due to unsatisfactory placement, number of pulses (for each pair of electrodes), probe length, space between probes, pulse voltage (amplitude, Volt), pulse length (μsec), pulse interval (ms) will be carefully noted. All complications (cardiac and non-cardiac) will be carefully registered and monitored.

Specific attention will be paid to the placement of electrodes close to bile ducts as previous research demonstrated that biliary strictures may occur when needles are placed within 3 mm of the bile ducts [29, 42].

Post RE treatment

Patients will be monitored on the recovery and surgical wards daily, according to current medical practice. Patients with endoscopic or percutaneous plastic drains will be evaluated for definitive metal stents (fully-, partially- or uncovered self-expanding metal stents) or removal of drains if obstruction appears to be treated by RE in all patients through an endoscopic or percutaneous approach at least 7 days after the RE procedure. This 7-day window is built in to avoid manipulation of the biliary tree immediately after RE. Bile ducts to atrophic liver lobes will not be drained. Following exploratory laparotomy and open RE, patients will undergo treatment in an enhanced recovery program. Patients will be monitored on the recovery and the surgical ward daily and discharged when fully recovered from the laparotomy, according to current medical practice.

General treatment

Patients with advanced PHC generally receive optimal palliative chemotherapy and adequate biliary drainage with metal stenting. In the current study, patients undergo local ablative therapy of the tumor. As it may be difficult to distinguish local RE-related effects on computed tomography scans or MRI from residual tumor tissue or tumor progression, it was decided that all patients in the current study will be proposed to receive palliative chemotherapy.

Palliative chemotherapy

All patients will be seen by the medical oncologist at MSKCC prior to intraoperative RE is performed, and palliative chemotherapy will be discussed. Patients will be offered optimal palliative chemotherapy according to medical oncology preferences. Palliative chemotherapy is not mandatory to participate in the trial, as some patients will not be eligible due to ongoing

cholangitis. Palliative chemotherapy post procedure is preferably started within 6 weeks after IRE when the patient has recovered from definitive metal biliary stent placement. The start of chemotherapy may be postponed in the event of IRE- or biliary drainage-related complications. However, delay of start to chemotherapy is not expected. In fact, we suspect that patients will be likely have a better chance of being treated with chemotherapy and for a longer duration of time, due to stent patency.

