12.0 CRITERIA FOR THERAPEUTIC RESPONSE/OUTCOME ASSESSMENT

The primary endpoint is biliary drainage patency. This will be measured as a marker of therapeutic response. Biliary drainage patency in patients with metal stents is defined as the period between RE treatment and stent occlusion or patient death. Occlusion of the stent is a clinical event. This is defined as recurrent jaundice with cholestasis, cholangitis (fever, increase in serum bilirubin, leukocytosis), stent failure that leads to replacement of a stent, or need to insert a new drain or stent within 4 months. Biliary drainage patency failure in patients that with plastic drains is defined as patients that cannot have plastic drain removed within 1.5 months of the RE.

The patients and caregivers are told about the symptoms of cholangitis and are asked to contact our hospital immediately in case of signs of obstruction. If stent obstruction is suspected, ERC will be performed and stents are changed if necessary.

Tumor response will not be evaluated in this trial by imaging via RECIST criteria as Klatskin tumors are difficult to measure as they are growing along the biliary tract.

Subjective evaluation of the ablation zone to determine the appearance of an RE associated ablation zone in the hilar area will be performed on postoperative scans.

Persistent disease is defined as residual tumor enhancement on the first post-treatment imaging study, and local recurrence is defined as an enhancing tumor within 1 cm of an ablation zone.

As a secondary endpoint we are measuring overall survival. If there is a response to our treatment, we would expect there may be a longer overall survival.

Response on blood biomarker is defined as decrease of blood marker by >20% from the pre-treatment value.

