14.1 BIOSTATISTICS

The primary objective of this study is to assess biliary drainage patency after IRE treatment of hilar cholangiocarcinoma. In patients with plastic percutaneous drains this is defined as ability to remove plastic biliary drains within 15 months of the IRE procedure without need for reinsertion of a drain or stent. For patients with metal stents in place the definition of patent biliary drainage is 4-months without cholangitis post IRE procedure.

We will enroll 20 patients. Mean patency is approximately 1.5 months for plastic stents and 4 months for metal stents. Assuming an exponential distribution time to failure, we extrapolate that the patency rate at 15 months for plastic stents and at 4 months for metal stents will approximately be 37% and we will use this number as our historical control rate. If 10 or more of the 20 patients we plan to enroll display patency (at 1.5 months for plastic and 4 months for metal stents) then we will recommend IRE for further study. This decision rule has 8% Type I error and 12% Type II error for distinguishing between patency rates of 37% and 65%.

The secondary outcomes of interest are:

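### The primary endpoint does not score consistently a patient whose plastic drain is exchanged for a metal stent after IRE, a step the treatment plan foresees

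*Combined protocol and SAP*

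**What the plan says.** Section 9.0 (post-IRE treatment) states: "Patients with endoscopic or percutaneous plastic drains will be evaluated for definitive metal stents". The alternative it names is removal, if the obstruction appears to have been treated. Either step takes place "through an endoscopic or percutaneous approach at least 7 days after the RE procedure". The chemotherapy text in the same section says that treatment after the procedure is "preferably started within 6 weeks after IRE when the patient has recovered from definitive metal biliary stent placement".

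The endpoint depends on the device:

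- **Plastic, Sections 1.0, 2.1 and 14.1.** Success in patients with percutaneous plastic drains is the "ability to remove plastic biliary drains within 1.5 months of the IRE procedure without need for reinsertion of a drain or stent". (The text of Section 14.1 shows 15 months in places. I read this as 1.5, which the same section also gives.)
- **Plastic, Section 12.0.** Failure is "defined as patients that cannot have plastic drain removed within 1.5 months of the RE". There is no condition on reinsertion.
- **Metal, Sections 1.0, 2.1 and 14.1.** "For patients with metal stents in place the definition of patent biliary drainage is 4-months without cholangitis post IRE procedure".
- **Metal, Section 12.0.** "Biliary drainage patency in patients with metal stents is defined as the period between RE treatment and stent occlusion or patient death".

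Section 14.1 pools both device groups into one count. IRE is recommended for further study if at least 10 of 20 patients are patent, against a control rate of 37%.

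**The concern.** Device type decides which definition and which time window a patient gets, yet no section says when device type is fixed, and the treatment plan can change it after IRE. Suppose a plastic drain is exchanged for a metal stent on day 20. Three of the four endpoint sections make this a failure on their plain wording. Section 12.0 does not. If the patient is instead treated as a metal-stent case, a post-treatment decision by the clinical team has changed the endpoint.

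Section 9.0 ties drain removal to the obstruction appearing treated, so exchanges are likely to include patients in whom IRE did not remove the need for a device. A reading that does not count them as failures can credit the new stent's performance to IRE. With one go/no-go count from 20 patients, a few such cases can decide the result.

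There is a smaller gap alongside. The full plastic definition names only percutaneous drains, while Section 9.0 expects endoscopic ones too. Device type is also absent from the baseline parameters listed in Section 10.0.

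**Working it through.** **1. Side-by-side reading of the day-20 exchange**

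| Text applied | Score |
|---|---|
| Sections 1.0, 2.1, 14.1, plastic clause | Failure, if the new metal stent counts as reinsertion of a stent |
| Section 12.0, plastic sentence | Not a failure: the plastic drain came out within 1.5 months |
| Metal clause (all four sections), if group may change after IRE | Undecided until 4 months, counted from IRE |

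Day 7 is the earliest time for an exchange and 1.5 months is about 45 days, so an exchange can fall well inside the window.

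**2. The plan's own figures**

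Inputs from Section 14.1: n = 20, cut-off 10, control rate 37%, target rate 65%, stated Type I error 8% and Type II error 12%.

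- Control rate: exp(−1) = 36.8%, which agrees with 37%.
- Cut-off 10: P(Bin(20, 0.37) ≥ 10) = 16.5%; P(Bin(20, 0.65) ≤ 9) = 5.3%.
- Cut-off 11: 7.8% and 12.2%.

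The stated error rates therefore belong to a cut-off of 11. That is a separate matter, and the present point does not depend on it. I use 10, as written.

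**3. Sensitivity to scoring**

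Let k be the number exchanged (an assumption; the documents give none), with the other 20 − k patients each patent with probability p.

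- Exchanges scored as failures: P(Bin(20 − k, p) ≥ 10).
- Exchanges scored as successes: P(Bin(20 − k, p) ≥ 10 − k).
- Exchanges treated as metal cases with the same p: unchanged, 16.5% at p = 0.37.

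| k | p = 0.37, failures | p = 0.37, successes | p = 0.65, failures | p = 0.65, successes |
|---|---|---|---|---|
| 2 | 8.5% | 33.5% | 86.1% | 97.9% |
| 3 | 5.6% | 44.9% | 78.7% | 98.8% |

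With a cut-off of 11 and k = 2, the p = 0.37 figures are 3.3% and 18.4%.

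**4. What the p = 0.37 columns assume**

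Fixing the score of k patients moves the overall expected rate away from 37%.

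- Failures: 18 × 0.37 / 20 = 33.3% for k = 2; 17 × 0.37 / 20 = 31.45% for k = 3.
- Successes: (2 + 18 × 0.37) / 20 = 43.3%; (3 + 17 × 0.37) / 20 = 46.45%.

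If exchanges are failures but the overall expectation is held at 20 × 0.37 = 7.4 successes, the remaining patients have rate 7.4/18 = 41.1% or 7.4/17 = 43.5%. The chance of reaching 10 is then 15.7% or 15.2%, close to the 16.5% of the rule as written.

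**The case against.** The strongest reply is that the protocol already answers the question. Three sections carry the reinsertion condition, and Section 12.0 may simply be shorthand for it. Section 9.0 says that a metal stent is no contraindication to IRE, so patients can enter with one, and Section 12.0 starts the metal-stent clock at IRE. Both suggest that the metal group means metal at IRE. This largely stands: the readings are not equally supported, and failure is the plain one. But Section 12.0 is the outcome-assessment section and lacks the condition, a planned exchange need not be read as reinsertion, and the time at which the group is fixed is only implied.

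Four stronger conclusions might be inferred, and the documents do not support them.

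- **That Section 12.0 makes the exchange a success.** It gives one failure condition for plastic drains and does not define success. The success columns above are an outer bound.
- **That exchange is the usual course.** Patients are evaluated for a metal stent or for removal. The description of metal stenting as general practice concerns advanced disease at large. No frequency is given.
- **That moving patients to the metal endpoint raises the no-effect rate above 37%.** For a stent placed d months after IRE, the plan's 4-month mean alone gives exp(−(4 − d)/4), which exceeds exp(−1). This assumes no failure before placement. Applying the plan's 1.5-month plastic mean to that interval gives exp(−d/1.5 − (4 − d)/4), which is below exp(−1). The direction of bias is not established.
- **That strict scoring sharply cuts the false-positive rate.** That fall comes from the lower overall rate shown in step 4 of the working.

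The endoscopic gap is also narrow: Section 12.0 and the decision rule in Section 14.1 refer to plastic devices without limiting them to percutaneous ones. Metal stent patency is listed as a secondary outcome in Section 1.0, though not in Section 2.1, so part of the descriptive need is already met.

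**Conclusion.** The point holds as an inconsistency in the definition of the primary endpoint. A foreseen step within the endpoint window is a failure on the plain wording of Sections 1.0, 2.1 and 14.1, is not a failure in Section 12.0, and could move the patient to a different endpoint because the time of group assignment is not stated.

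For 2 exchanges, the chance of recommending IRE lies between 8.5% and 33.5%, and for 3 between 5.6% and 44.9%. These ranges rest on an assumed number of exchanges, the other patients at 37%, a cut-off of 10, and all exchanges scored alike. They show that scoring can decide the count; they do not estimate the trial's true error rates. The contradiction itself rests on the text alone.

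**What to change.** Reconcile Sections 1.0, 2.1, 12.0 and 14.1 with one scoring rule, set before outcomes are known:

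- The endpoint group is fixed by the device in place at the start of IRE and does not change.
- Endoscopic and percutaneous plastic drains together form the plastic group.
- For scoring only, and in line with the wording already in Sections 1.0, 2.1 and 14.1, a plastic drain replaced by a metal stent within 1.5 months counts as not patent. Add the reinsertion condition to Section 12.0.
- Patients with both device types at IRE are assigned to one group in advance. Requiring both definitions would break the benchmark: if the two were independent, the no-effect rate would be 0.37 × 0.37, about 14%.

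Record device type at IRE, report the number exchanged, and give a sensitivity count under the alternative scoring.

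The cost is wording in four sections and one baseline data field, with no added patients or procedures. The downside is that the observed success count may be lower than under the lenient reading. This concerns scoring only and says nothing about whether or when a stent should be placed.
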